15.1.3 Sensitivity Analysis of Primary Effectiveness Variable

The same model as in the primary analysis will be fitted for PPS. In addition to descriptive statistics for LDL-C at each visit and its percentage change from baseline by treatment group, LS means for each treatment group with corresponding SEs and treatment differences of LS means with corresponding two-sided 95% CIs and p-value will be presented.

Sensitivity analysis using the LOCF imputation method will be performed for the primary endpoint, percent change from baseline in LDL-C. The same model as in the primary analysis will be fitted for the sensitivity analysis (LOCF).

15.2 Secondary Effectiveness

15.2.1 Secondary Effectiveness Variables & Derivations

To evaluate the clinical effectiveness of early add-on of ezetimibe with atorvastatin in very high-risk patients, following endpoints will be examined.

- Proportion of patients achieving LDL-C goal of <55 mg/dL at 6 weeks and 12 weeks of treatment.
- Proportion of patients achieving LDL-C goal of <70 mg/dL at 6 weeks and 12 weeks of treatment.

Document: Document path and title

Template No.: CCI

Reference: CCI

Effective Date: 15Oct2021

- Percentage change in LDL-C from baseline to week 12
- Percentage change in HDL-C, non-HDL-C, triglycerides, and total cholesterol from baseline to week 6 and week 12

Percentage change in LDL-C, HDL-C, non-HDL-C, triglycerides, and total cholesterol will be derived as described in section 7.4.

LDL-C, HDL-C, non-HDL-C, triglycerides, and total cholesterol values at baseline , Week 6 and Week 12 will be used.

15.2.2 Missing Data Methods for Secondary Effectiveness Variable(s)

No missing data imputation will be used for the analysis of the secondary effectiveness variables.

15.2.3 Analysis of Secondary Effectiveness Variables

All secondary endpoint analyses will be performed on the FAS.

The number and percentage of patients achieving LDL-C goal of < 55 mg/dL and LDL-C goal of < 70 mg/dL at 6 weeks and 12 weeks will be presented by treatment group and tested using Chi-square test or Fisher's exact test as appropriate. The difference in the percentage will be presented with its corresponding 95% CI and p-value.

The continuous secondary endpoints (except triglycerides) will be analyzed by fitting ANCOVA models with treatment group (Eze/Ato, Ato) and history of statin administration (Yes, No) as fixed effects and baseline value of interest as a covariate. In addition to descriptive statistics for variables of interest at each visit and its percentage change at a period from baseline by treatment group, LS means for each treatment group with corresponding SEs and treatment differences of LS means with corresponding two-sided 95% CIs and p-value will be presented. The ANCOVA model will be fitted separately at 6 weeks and 12 weeks.

A nonparametric approach will be used for the analysis of triglycerides (percent change from baseline). The Hodges-Lehmann method will be used to estimate the median difference and its corresponding 95% CI for percent changes between the treatment groups.

Document: Document path and title

Template No.: CCI

Reference: CCI

Effective Date: 15Oct2021

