5.1 Inclusion Criteria

Participants are eligible to be included in the study only if all of the following criteria apply:

1. Patients who are ≥ 30 years old.
2. Patients with very high-risk*
*: clinical or unequivocal on imaging ASCVD. ASCVD includes previous ACS (MI or UA), stable angina, coronary revascularization (percutaneous coronary intervention (PCI), coronary artery bypass graft surgery (CABG), and other arterial revascularization procedures), stroke and transient ischaemic attack (TIA), and peripheral arterial disease (Mach F 2020).
3. Patients (a) who failed to achieve LDL-C lower than 70 mg/dL with low and/or moderate intensity^{\$} statin mono therapy for ≥ 4 weeks or (b) who are statin-naïve or have not been on a stable (unchanged) statin regimen for at least 4 weeks prior to enrollment.
\$: rosuvastatin < 20 mg, atorvastatin < 40 mg, and all dose of pitavastatin, simvastatin, lovastatin, pravastatin, and fluvastatin (Stone NJ 2014).
4. Patients with LDL-C levels ≥ 70 mg/dL
5. Patients who are willing to maintain TLC throughout the study.
6. Patients who are willing to provide written informed consent prior to study enrollment.

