4.2 Sample Size

The number of patients in each treatment group is about 57, assuming that the treatment difference in percentage change in LDL-C between Ezetimibe/Atorvastatin and Atorvastatin would be 10% with an SD of 19%. This calculation is based on a two-sided significance level $\alpha = 0.05$, power $1-\beta = 0.80$ with a randomization ratio $\lambda = 1$. Considering the dropout rate of 10%, 63 patients for each group and thus, a total of 126 patients will be randomized in this study.

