7.2 Baseline

Except for the lipid parameters for which Visit 1 measurement will be used as the baseline, baseline is defined as the last non-missing measurement taken prior to reference start date. In the case where the last non-missing measurement and the reference start date coincide, that measurement will be considered pre-baseline, but Adverse Events (AEs), medications, and medical procedures commencing on the reference start date are considered post-baseline.

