8.2 Statistical Tests and Confidence Intervals

For continuous efficacy variables (except triglycerides), the statistical comparisons between treatment groups are performed using an analysis of covariance (ANCOVA) with treatment group and history of statin administration as factors and the corresponding baseline as a covariate. For categorical efficacy variables, the statistical significance of the differences between treatment groups is tested using Chi-square test or Fisher's exact test. All the statistical tests use a two-sided test at the significance level of 0.05.

Due to the known distribution of triglycerides, normality assumption is usually difficult to satisfy. A nonparametric approach will be used for the analysis of percent change from baseline for triglycerides. The Hodges-Lehmann method will be used to estimate the median difference and its corresponding 95% CI for percent changes between the treatment groups.

Inferential conclusion will be drawn only for primary endpoint based on p-value at 0.05 significance level as described in section 15.1.2 of this analysis plan.

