8.3 Adjustments for Covariates and Factors to be Included in Analyses

The following covariates and factors are used in ANCOVA models. For details of their inclusion in the models, see the specific analysis section.

- Baseline value of interest
- Treatment group: Eze/Ato, Ato
- History of statin administration: Yes (≥ 4 weeks), No (< 4 weeks, naïve)

Document: Document path and title

Template No.: CCI

Reference: CCI

Effective Date: 15Oct2021

- Yes if 'Is the patient under statin treatment?' is 'Yes for 4 weeks or more from today' from 'Medical history related to dyslipidemia risk factors' page of eCRF
- No if 'Is the patient under statin treatment?' is 'Yes, but for less than 4 weeks from today' or 'No' from 'Medical history related to dyslipidemia risk factors' page of eCRF

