15.2.4 Sensitivity Analysis of Secondary Effectiveness Variables

The same models as in the secondary analysis will be fitted for PPS, and corresponding descriptive statistics will be also presented.

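### The Table 128 footnote divides goal attainment by all patients, so six up-titration tables count a missing Week 12 LDL-C as not at goal; a baseline-adjusted estimate beside the main goal comparisons would be a cheap, precision-only addition

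*SAP*

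**What the plan says.** **Goal rates and missing values.** SAP 15.2.2 states: "No missing data imputation will be used for the analysis of the secondary effectiveness variables". The Table 20 shell in SAP Appendix 2 matches, with percentage = 100 * (n / Nx), where Nx counts patients with a value. The Table 128 shell also prints an Nx row, but its footnote gives 100 * (n / N), with N described as the patients in the FAS. Tables 129 and 142-145 are to follow Table 128. Tables 130 and 131 are to follow Table 20.

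**Comparison of goal rates.** SAP 15.2.3 and Protocol 9.3.3 have the percentages "presented by treatment group and tested using Chi-square test or" Fisher's exact test, with a difference, 95% CI and p-value. No covariate enters. For the continuous endpoints other than triglycerides, SAP 15.2.3 uses ANCOVA with statin history and the baseline value. SAP 8.3 ties those terms to that model: "The following covariates and factors are used in ANCOVA models".

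**Status.** SAP 8.2: "Inferential conclusion will be drawn only for primary endpoint based on p-value at 0.05 significance level". The goal endpoints are secondary, and the up-titration tables come under exploratory effectiveness (SAP 15.3).

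**The concern.** Dividing by N amounts to imputing failure for anyone without a Week 12 value, which the SAP text excludes. The affected tables would show lower rates than Table 20 logic gives. If missingness differs between arms, they would show a treatment difference that the observed data do not contain. The two <70 mg/dL halves, which will naturally be read side by side, would not be on the same basis.

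The second matter is efficiency. Whether a patient crosses a fixed threshold depends on where that patient starts. Entry requires only a minimum ("Patients with LDL-C levels ≥ 70 mg/dL"), so starting values can vary widely. Baseline LDL-C and statin history are both collected, yet the goal comparison uses neither. At stake is the width of the reported CI, not its validity.

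**Working it through.** **1. Denominators side by side (SAP Appendix 2)**

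| Up-titrated at Week 6 | Goal (mg/dL) | Tables (FAS, PPS) | Shell followed | Denominator |
|---|---|---|---|---|
| Yes | <55 | 128, 129 | 128 | N |
| Yes | <70 | 130, 131 | 20 | Nx |
| No | <55 | 142, 143 | 128 | N |
| No | <70 | 144, 145 | 128 | N |

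Six tables use N. Tables 20-23 and the other subgroup goal tables use Nx.

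**2. Size of the denominator error**

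Take N as the subgroup count and let m = 1 - Nx/N be the share missing at Week 12. Then n/N = (Nx/N) x (n/Nx) = (1 - m) x observed rate.

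The documents do not give m for the period between Visit 3 and Week 12. With m assumed to be 3% to 10% and an observed rate of 60%:

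- m = 3%: 0.97 x 60 = 58.2%
- m = 10%: 0.90 x 60 = 54.0%
- m = 10% at <70 mg/dL: 60% prints as 60% in Tables 130-131 and as 54% in Tables 144-145
- m = 3% in one arm and 10% in the other, equal observed rates of 60%: 58.2 - 54.0 = 4.2 points apart. For rates of 30% to 90% the gap is 0.07 x 30 = 2.1 to 0.07 x 90 = 6.3 points.

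**3. The plan's sample size, used in step 4**

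SAP 4.2 and Protocol 9.5 give difference 10, SD 19, two-sided 0.05 and power 0.80: 2 x (1.96 + 0.842)^2 x 19^2 / 10^2 = 56.69, so 57 per arm. Then 56.69 / 0.9 = 62.99, which matches the plan: "Considering the dropout rate of 10%, 63 patients for each group". No power is stated for goal attainment.

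**4. What adjustment could gain (simulation, 4,000 trials per scenario, 57 per arm)**

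From the documents: difference 10, SD 19, and the control and test changes of -10% and -20% in Protocol 9.5.

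Assumed:
- 20 of 57 per arm (35%, within the 40% cap) in statin stratum (b).
- Baseline LDL-C in strata (a)/(b) of N(90,18)/N(120,30), N(95,20)/N(125,30) or N(105,25)/N(135,35), truncated at 70.
- Control change in (a)/(b) of -10/-10, -20/-35 or -25/-45.
- Within-stratum correlation r between baseline and percentage change. Percentage change = mean + 19 x (r z + sqrt(1 - r^2) e), with z the standardised baseline.

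A negative r is plausible because the value that qualifies a patient is also the baseline (SAP 7.2: "Except for the lipid parameters for which Visit 1 measurement will be used as the baseline"). Measurement error alone, at an assumed within-person CV of 5-10%, gives r of -0.04 to -0.18.

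The adjusted estimate is a standardised risk difference from a logistic model. It is used only if at least 20 patients (both arms together) are at goal and at least 20 are not. Reduction in its SE at Week 6, among trials where the model is used:

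| r | <70 mg/dL | <55 mg/dL |
|---|---|---|
| 0 | 8-13% | 5-8% |
| -0.15 | 4-9% | 3-5% |
| -0.3 | 2-6% | 1-3% |
| -0.5 | 0-3% | 0-2% |

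At Week 12 (assuming a further 5 or 10 point fall after up-titration and residual correlation 0.6), the reduction runs from 6-12% at r = 0 down to 0-5% at r = -0.5 for <70, and from 4-7% down to 0-2% for <55.

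Example at <70, Week 6 (first baseline set, control -20/-35): the CI half-width goes from 17.9 to 16.3 points at r = 0, 17.8 to 17.4 at r = -0.3, and 17.7 to 17.7 at r = -0.5.

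**5. How often the model could be used**

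Share of simulated trials in which the 20-patient rule blocks the model, across baseline sets and r:

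- <55 with the documents' -10% v -20%: 99-100%
- <70 with the same changes: 0-96%
- <55 with control changes of -20/-35: 2-94%

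Hand check of the first line at an assumed baseline of 90 mg/dL. Reaching 55 needs a change of (55 - 90)/90 = -38.9%. Test arm: Phi((-38.9 + 20)/19) = Phi(-0.99) = 0.16. Control: Phi((-38.9 + 10)/19) = Phi(-1.52) = 0.064. Expected at goal: 57 x 0.16 + 57 x 0.064 = about 13, below 20.

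**The case against.** **On the denominator.** Only six exploratory tables are touched, the SAP text already bars imputation, and the Nx row lets a reader recover n/Nx. Up-titration is decided after randomisation, so comparisons within these subgroups are descriptive at best. All of that stands and limits the consequence. It does not make the footnote right: a programmer following it would print rates that contradict SAP 15.2.2.

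Two stronger readings are tempting.

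- A reader might take the planned 10% dropout as the Week 12 missing share. The documents do not support this. That figure inflates the sample for the Week 6 primary endpoint, and up-titration status requires a dose decision at Visit 3 (SAP 8.5), so only loss between Visit 3 and Week 12 counts.
- A reader might take N literally as the whole FAS, which would also scale each rate by the subgroup's share. Table 20 carries the same description of N and is reused for the PPS and other subgroups, so this looks like carried-over wording.

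**On adjustment.** Protocol and SAP agree on chi-square or Fisher, adjusted LDL-C comparisons are already planned at both visits, and goal rates by statin history have their own tables. The gain rests on baselines and an r that the documents do not give. A separate simulation with other assumed baselines, r = 0 and no sparse-data rule gave SE reductions of 3-11% at SD 19. It reached 21% only with wide baselines and SD 15, which is not the plan's SD. In one <55 scenario power fell, from 0.30 to 0.25. The 20-patient threshold is a choice, and it makes the availability of the estimate depend on the data. Simulated type I error at <70 was 0.022-0.056 for the planned test and 0.022-0.062 for the adjusted one. These points stand and are why the adjusted estimate should be supplementary only.

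**Conclusion.** The Table 128 footnote is wrong as written. It conflicts with SAP 15.2.2 and with Table 20, and it puts the two <70 mg/dL up-titration halves on different denominators. The understatement equals the missing share times the observed rate: 1.8 to 6.0 points at 60% under the assumed 3-10%. It does not reach Tables 20-23 or the primary endpoint.

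The unadjusted goal comparison is not an error. A reader might infer that it is invalid or weakens the trial's conclusion. Neither follows, because the test is valid and SAP 8.2 reserves inference for the primary endpoint. Adjustment would trim the SE by about 0-13% when the model can be used. It would give nothing when the sparse-data rule applies, which is nearly always at <55 mg/dL if the -10% v -20% changes hold. Overall the point is minor. The denominator part is certain from the text; the size of the precision gain depends on the assumptions.

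**What to change.** **Footnote (should be done).** In the Table 128 shell, change the percentage to 100 * (n / Nx) and define N as the number of patients in the subgroup. This corrects Tables 128, 129 and 142-145 together. The cost is one footnote.

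**Supplementary estimate (optional, cheap).** In SAP 15.2.3, keep the crude difference, its CI and chi-square/Fisher as the planned analysis. For Tables 20 and 22, add a standardised risk difference with 95% CI from a logistic model with treatment, statin history and baseline LDL-C. Report it only when at least 20 patients are at goal and at least 20 are not. State that PPS and subgroup goal tables stay unadjusted, since SAP 15.2.4 ("The same models as in the secondary analysis will be fitted for PPS") and SAP 15.3 would otherwise carry the model into them. Record the addition in SAP 4.5. The cost is SAP wording and extra rows in two tables. The downside is a model-based estimate that may be available for one goal and not the other; the crude result is there for both.

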9.3.3 Secondary Endpoints

All secondary endpoint analyses will be performed on the FAS and PPS.

The number and percentage of patients achieving LDL-C goal of < 55 mg/dL and LDL-C goal of < 70 mg/dL at 6 weeks and 12 weeks will be presented by treatment group and tested using Chi-square test or Fisher's exact test as appropriate. The difference in the percentage will be presented with its corresponding 95% CI and p-value.

For continuous secondary variables, the percentage change from baseline at time point of interest will be analyzed by fitting ANCOVA model with treatment group as a factor and its corresponding baseline and history of statin administration as a covariate. Estimates of LS mean and SE for within-treatment effects and treatment differences along with corresponding two-sided 95% CI and p-value will be provided. In addition, descriptive statistics will be presented for outcome of interest at each visit and for percentage change from baseline.

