Based on this, the number of patients in each treatment group calculated by the formula below is about 57 under the assumption of two-sided significance level $\alpha = 0.05$, power $1-\beta = 0.80$ with a randomization ratio $\lambda = 1$. Considering the dropout rate of 10%, 63 patients for each group and thus, a total of 126 patients will be randomized in this study.

$$n = \frac{(\gamma + 1)(Z_\alpha + Z_\beta)^2 \sigma^2}{\gamma(\mu_t - \mu_c)^2} = \frac{(1 + 1)(1.96 + 0.842)^2(19)^2}{(-10)^2} = 56.69$$

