	[Min – Max]	[00.00 - 00.00]	[00.00 - 00.00]
b. ANCOVA [a]	LS Mean (SE)	00.00 (00.00)	00.00 (00.00)
	95% CI for LS Mean	(00.00, 00.00)	(00.00, 00.00)
	LS Mean Difference	00.00	00.00
	95% CI for Difference	(00.00, 00.00)	(00.00, 00.00)
	p-value	0.000	0.000

FAS: full analysis set; HDL-C: high-density lipoprotein cholesterol; SD: standard deviation; Q1: 1st quartile; Q3: 3rd quartile; Min: minimum; Max: maximum; ANCOVA: analysis of covariance; LS: least squares; SE: standard error; CI: confidence interval.

N = the number of patients in FAS; Nx = the number of patients without missing values.

[a] ANCOVA model with treatment group (Eze/Ato, Ato), history of statin administration (Yes, No), and baseline HDL-C.

Table 27. Percentage Change in HDL-C from Baseline to Week 6 and 12 (PPS)

Repeated style; see Table 26.

Document: Document path and title

Template No.: CCI

Reference: CCI

Effective Date: 15Oct2021

Table 28. Percentage Change in non-HDL-C from Baseline to Week 6 and 12 (FAS)

Repeated style; see Table 26.

Table 29. Percentage Change in non-HDL-C from Baseline to Week 6 and 12 (PPS)

Repeated style; see Table 26.

Document: Document path and title

Template No.: CCI [REDACTED]

Reference: CCI [REDACTED]

Effective Date: 15Oct2021

Table 30. Percentage Change in Triglycerides from Baseline to Week 6 and 12 (FAS)

Item	Statistics	Eze/Ato (N=00)	Ato (N=00)
Baseline	Nx	00	00
	Mean \pm SD	00.00 \pm 00.00	00.00 \pm 00.00
	Median	00.00	00.00
	Q1, Q3	00.00, 00.00	00.00, 00.00
	[Min – Max]	[00.00 - 00.00]	[00.00 - 00.00]
Week 6	Nx	00	00
	Mean \pm SD	00.00 \pm 00.00	00.00 \pm 00.00
	Median	00.00	00.00
	Q1, Q3	00.00, 00.00	00.00, 00.00
	[Min – Max]	[00.00 - 00.00]	[00.00 - 00.00]
Week 12	Nx	00	00
	Mean \pm SD	00.00 \pm 00.00	00.00 \pm 00.00
	Median	00.00	00.00
	Q1, Q3	00.00, 00.00	00.00, 00.00
	[Min – Max]	[00.00 - 00.00]	[00.00 - 00.00]
Percentage change from baseline to Week 6			
c. Descriptive	Nx	00	00
	Mean \pm SD	00.00 \pm 00.00	00.00 \pm 00.00
	Median	00.00	00.00
	Q1, Q3	00.00, 00.00	00.00, 00.00
	[Min – Max]	[00.00 - 00.00]	[00.00 - 00.00]
d. +Nonparametric [a]	Difference in Medians	00.00	
	95% CI for Difference	(00.00, 00.00)	
Percentage change from baseline to Week 12			
c. Descriptive	Nx	00	00
	Mean \pm SD	00.00 \pm 00.00	00.00 \pm 00.00
	Median	00.00	00.00
	Q1, Q3	00.00, 00.00	00.00, 00.00
	[Min – Max]	[00.00 - 00.00]	[00.00 - 00.00]
d. Nonparametric [a]	Difference in Medians	00.00	
	95% CI for Difference	(00.00, 00.00)	

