Repeated style; see Table 26.

Document: Document path and title

Template No.: CCI [REDACTED]

Reference: CCI [REDACTED]

Effective Date: 15Oct2021

Table 100. Proportion of patients achieving LDL-C goal of <55 mg/dL at Week 6 and 12 (with Statin Administration History in FAS)

Repeated style; see Table 20.

Table 101. Proportion of patients achieving LDL-C goal of <55 mg/dL at Week 6 and 12 (with Statin Administration History in PPS)

Repeated style; see Table 20.

Table 102. Proportion of patients achieving LDL-C goal of <70 mg/dL at Week 6 and 12 (with Statin Administration History in FAS)

Repeated style; see Table 20.

Table 103. Proportion of patients achieving LDL-C goal of <70 mg/dL at Week 6 and 12 (with Statin Administration History in PPS)

Repeated style; see Table 20.

Table 104. Percentage Change in LDL-C from Baseline to Week 6 and 12 (without Statin Administration History in FAS)

Repeated style; see Table 26.

Table 105. Percentage Change in LDL-C from Baseline to Week 6 and 12 (without Statin Administration History in PPS)

Repeated style; see Table 26.

Table 106. Percentage Change in HDL-C from Baseline to Week 6 and 12 (without Statin Administration History in FAS)

Repeated style; see Table 26.

Table 107. Percentage Change in HDL-C from Baseline to Week 6 and 12 (without Statin Administration History in PPS)

Repeated style; see Table 26.

Table 108. Percentage Change in non-HDL-C from Baseline to Week 6 and 12 (without Statin Administration History in FAS)

Repeated style; see Table 26.

Document: Document path and title

Template No.: CCI

Reference: CCI

Effective Date: 15Oct2021

Table 109. Percentage Change in non-HDL-C from Baseline to Week 6 and 12 (without Statin Administration History in PPS)

Repeated style; see Table 26.

Table 110. Percentage Change in Triglycerides from Baseline to Week 6 and 12 (without Statin Administration History in FAS)

Repeated style; see Table 30.

Table 111. Percentage Change in Triglycerides from Baseline to Week 6 and 12 (without Statin Administration History in PPS)

Repeated style; see Table 26.

Table 112. Percentage Change in Total Cholesterol from Baseline to Week 6 and 12 (without Statin Administration History in FAS)

Repeated style; see Table 26.

Table 113. Percentage Change in Total Cholesterol from Baseline to Week 6 and 12 (without Statin Administration History in PPS)

Repeated style; see Table 26.

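### SAP Table 111 sends one triglyceride analysis to the excluded ANCOVA shell, and triglycerides alone among the continuous lipids are compared without baseline or statin-history adjustment

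*SAP*

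**What the plan says.** **Protocol 9.3.3** plans ANCOVA for the continuous secondary variables, with treatment as a factor and "its corresponding baseline and history of statin administration as a covariate". It makes no exception for triglycerides.

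**SAP 15.2.3** keeps that model for the other lipids: "The continuous secondary endpoints (except triglycerides) will be analyzed by fitting ANCOVA models with treatment group (Eze/Ato, Ato) and history of statin administration", plus baseline. For triglycerides it substitutes a nonparametric comparison: "The Hodges-Lehmann method will be used to estimate the median difference and its corresponding 95% CI for percent changes between the treatment groups". No covariate or stratum is named. SAP 8.2 says the same and gives non-normality as the reason. SAP 8.3 attaches its covariates to the ANCOVA models only. SAP 15.3 applies the same methods within subgroups.

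**SAP 8.6** stratifies randomisation by institution and statin history. **SAP 4.5** declares no change from the protocol's analysis.

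**SAP Appendix 2.** Table 30 is the triglyceride shell. Its comparison row reads "Difference in Medians", under a nonparametric heading whose footnote names the Hodges-Lehmann method. Table 26 is the HDL-C shell, with ANCOVA LS means, a difference and a p-value. The shell titled "Table 111. Percentage Change in Triglycerides from Baseline to Week 6 and 12 (without Statin Administration History in PPS" refers the programmer to Table 26.

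**The concern.** Sections 8.2, 15.2.3 and 15.3 and the Table 111 shell give different instructions for the same endpoint. A programmer who follows the shell would fit ANCOVA and print a p-value in one triglyceride table. Its full-analysis-set twin, Table 110, would show a Hodges-Lehmann estimate and no p-value.

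The second point concerns the method. Skewness is a good reason to leave ANCOVA on the raw percentage change. It is not a reason to leave out baseline and the stratum, since an ANCOVA on the log scale deals with skewness and keeps both. What is at stake is some possible precision on one secondary endpoint, comparability with the other lipids, and a departure from the protocol that the section meant to declare such departures does not mention.

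**Working it through.** **1. Table pointers.** Appendix 2 has 18 triglyceride tables: 30, 31, 40, 41, 54, 55, 68, 69, 82, 83, 96, 97, 110, 111, 124, 125, 138 and 139. Table 30 is the shell. Of the other 17, 16 refer to Table 30 and one, Table 111, refers to Table 26. The revision history for version 1.3 lists Table 111 among the tables moved to the nonparametric layout, so the intent is clear. The error is in the current shell.

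**2. Adjustment by endpoint.** LDL-C, HDL-C, non-HDL-C and total cholesterol are analysed with treatment, statin history and own baseline. Triglycerides are analysed with treatment only.

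**3. The plan's own figure.** The documents give no triglyceride variance, effect or correlation. The only design figure is for LDL-C, where the difference "would be 10% with an SD of 19" percent: n = 2 × (1.96 + 0.842)² × 19² / 10² = 56.69, so 57 per group. This reproduces and is not affected. I use 57 per arm below.

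**4. Precision from adjustment (assumed R²).** If baseline and stratum explain a share R² of the variance, the interval width is multiplied by about √(1 − R²), and 57 patients count as 57 / (1 − R²).

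| Assumed R² | Width, adjusted / unadjusted | Effective n per arm |
|---|---|---|
| 0 | 1.00 | 57.0 |
| 0.05 | 0.975 | 60.0 |
| 0.10 | 0.949 | 63.3 |
| 0.20 | 0.894 | 71.2 |
| 0.30 | 0.837 | 81.4 |

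**5. Simulation (all inputs but the 57 assumed).** 3,000 trials per setting; log(Week X / baseline) with SD 0.45, mean −0.15 under control and −0.25 under test; 40% in the stratum without stable statin; stratum effects of 0, −0.1 and −0.2. The correlation is between log change and log baseline, in absolute value. The adjusted Hodges-Lehmann estimate is computed after removing the fitted baseline and stratum effects. SDs are shown for stratum effect 0; the last column covers all three stratum effects.

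| Correlation | SD, Hodges-Lehmann | SD, adjusted Hodges-Lehmann | SD, raw-scale ANCOVA | Adjusted / unadjusted Hodges-Lehmann |
|---|---|---|---|---|
| 0 | 6.93 | 7.01 | 8.31 | 1.01–1.03 |
| 0.3 | 6.90 | 6.80 | 7.97 | 0.98–0.99 |
| 0.5 | 6.89 | 6.29 | 7.25 | 0.91–0.94 |

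Across all settings the unadjusted Hodges-Lehmann SD was 0.83 to 0.95 of the raw-scale ANCOVA SD. The two target different quantities, however. Dividing each SD by its own average estimate gives 6.93/7.90 = 0.88 against 8.31/9.20 = 0.90 at correlation 0, and 6.89/7.78 = 0.89 against 7.25/8.95 = 0.81 at 0.5. No general ranking follows. The log-scale ANCOVA proposed below is on another scale and is not in this table.

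**6. Row label.** The Hodges-Lehmann estimate is the median of all between-arm pairwise differences. It equals the difference of the arm medians only in special cases, such as a pure location shift. In five skewed examples with assumed inputs the population values were −7.88, −8.02, −7.76 and −7.53 against −8.19, and −15.36 against −16.40. The gaps run from 0.17 to 1.04 points.

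**The case against.** The strongest defence is that the method is a stated and legitimate choice. SAP 8.2 gives the reason. The outcome is a percentage change, so baseline already enters it. Stratified randomisation balances statin history by design, and triglycerides are also reported within each statin-history group (Tables 96, 97, 110 and 111). Conclusions are confined to the primary endpoint, and Table 30 carries no p-value. The Table 111 pointer is one slip in an exploratory per-protocol subgroup table.

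Most of this stands, and it is why the Hodges-Lehmann estimate should stay. Two parts do not settle the matter. Dividing by baseline does not remove dependence of the change on baseline. Balance by design protects against bias but does not recover the variance that a prognostic covariate explains.

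A reader might go further and infer that the planned estimate is less precise than the protocol's ANCOVA. The documents do not support that. They give no triglyceride variance or baseline correlation, and with skewed data the unadjusted Hodges-Lehmann estimate can do as well or better. Nor did stratifying it by statin history alone reduce its SD in simulation with assumed inputs.

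A reader might also infer that the row label distorts the result. With 57 per arm and an assumed log-SD of 0.40, the Hodges-Lehmann estimate and the plain difference in medians differ within a trial by 3.2 points on average in absolute value. That is sampling scatter between two estimators (SDs about 6.3 and 8.1). The average signed gap is only about 0.1 to 0.4 points, and the Table 30 footnote already names the method.

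**Conclusion.** The point holds in two limited parts.

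- **Table 111 is wrong as written.** It contradicts sections 8.2, 15.2.3 and 15.3 and the other triglyceride tables. This rests on the text alone. It affects one exploratory table.
- **Triglycerides are the only continuous lipid endpoint analysed without baseline or statin history.** Protocol 9.3.3 adjusts for both, and SAP 4.5 declares no change. The lack of adjustment is a missed low-cost improvement rather than an error. The gain is measured against an unadjusted analysis only: none if the covariates are not prognostic, up to about 9% smaller SD in the simulation, and about 16% narrower intervals if R² reached 0.30. All of these rest on assumed inputs.

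The row label is an editorial matter. Nothing here touches the primary analysis or the sample size.

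**What to change.** 1. Point Table 111 to Table 30. This changes one number.
2. Keep the Hodges-Lehmann estimate and its interval as planned. Add to SAP 15.2.3 a supportive ANCOVA of log(Week X / baseline triglycerides), fitted separately at Weeks 6 and 12, with treatment, statin history and log baseline. Report the exponentiated treatment coefficient as a ratio of geometric means with 95% CI. The cost is one extra model and a second effect scale, which needs a footnote. Replacing the planned method outright would change the quantity estimated and is not needed.
3. In SAP 4.5, list the move of triglycerides from ANCOVA to Hodges-Lehmann. If the supportive model is not adopted, say in 15.2.3 that the estimate is unadjusted.
4. Optionally, rename the Table 30 row *Hodges-Lehmann shift estimate*.

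Trial conduct and data collection are unchanged. If the database is already locked, which the documents do not show, label the added model post hoc.
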